### **10.2 Data Clarification**

As part of the conduct of the trial, the Sponsor may have questions about the data entered by the site, referred to as queries. The monitors and the Sponsor are the only parties that can generate a query. All corrections and clarifications will be entered into the EDC system and will be identified by the person entering the information, the reason for the change, as well as the time of the changes made. If changes are made to a previously and electronically signed CRF, the investigator must confirm and endorse the changes.

### **10.3 Data Protection**

Seqirus respects the subjects' rights to privacy and will ensure the confidentiality of their medical information in accordance with all applicable laws and regulations.

The Sponsor as Data Controller according to the European Directive on the protection of individuals with regard to the processing of personal data and on the free movement of such data ([European Parliament, 1995](#)) confirms herewith compliance to Directive [95/46/EC](#) in all stages of Data Management.

## **11. RECORD RETENTION**

Investigators must retain all study records required by Seqirus and by the applicable regulations in a secure and safe facility. The Investigator must consult a Seqirus representative before disposal of any study records, and must notify the Sponsor of any change in the location, disposition, or custody of the study files. Essential documents must be retained for 15 years. "Essential documents" are defined as documents that individually and collectively permit evaluation of the conduct of a study and the quality of the data produced. These documents should be retained for a longer period, however, if required by the applicable national regulatory or institutional requirements.

Laboratory samples will be retained for a period of up to 15 years.

## 12. USE OF INFORMATION AND PUBLICATION

Seqirus assures that the key design elements of this protocol will be posted in a publicly accessible database such as clinicaltrials.gov, and in compliance with current regulations.

Seqirus also assures that key results of this clinical study will be posted in a publicly accessible database within the required time-frame from the end of study as defined in [Section 3.9, End of Study](#).

In accordance with standard editorial, ethical practices and current guidelines of Good Publication Practice ([Graf, 2009](#)), Seqirus will generally support publication of multicenter studies only in their entirety and not as individual center data. In this case, a Coordinating Investigator will be designated by mutual agreement prior to the start of the study. The Coordinating Investigator will also sign the clinical study report on behalf of the Principal Investigators ([CPMP, 2001](#)). Authorship will be determined by mutual agreement and in line with International Committee of Medical Journal Editors authorship requirements. Any formal publication of the study in which contribution of Seqirus personnel exceeded that of conventional monitoring will be considered as a joint publication by the investigator and the appropriate Seqirus personnel.

Seqirus must be notified of any intent to publish data collected from the study and prior approval from Seqirus must be obtained prior to submission for publication.

## 13. ETHICAL CONSIDERATIONS

### 13.1 Regulatory and Ethical Compliance

The study will be conducted in compliance with the protocol, GCP and applicable regulatory requirement(s).

This clinical study was designed and shall be implemented and reported in accordance with the ICH Harmonized Tripartite Guidelines for Good Clinical Practice, with applicable local regulations: including European Directive 2001/20/EC, US Code of Federal Regulations Title 21, and Japanese Ministry of Health, Labor, and Welfare. Seqirus codes on protection of human rights, and with the ethical principles laid down in the Declaration of Helsinki ([European Council 2001, US Code of Federal Regulations, ICH, 1997](#)).

### 13.2 Informed Consent Procedures

Eligible subjects may only be included in the study after providing written informed consent, as described in [Section 5.1.1, Informed Consent](#). Before the start of the study, the Investigator will have the informed consent and any other materials that will be provided to the subjects reviewed and approved by the IRB/EC. This review and approval will be documented and stored with other study documents. The Investigator or designee must fully inform the subject or legal representative of all pertinent aspects of the study. A copy of the written informed consent will be given to the subject or the designee. The subject/designee must be allowed ample time to ask about the details of the study and to make a decision as to whether or not to participate in the study. The subject (and/or legal representative(s) **must** sign the consent form indicating their agreement to participate in the study before any study-related procedures are conducted. The informed consent process may be conducted up to 10 days prior to vaccination on Day 1. If the subject and/or legal representative(s) is unable to read and write, a witness must be present during the informed consent discussion and at the time of informed consent signature.

Prior to the start of the study, Seqirus will provide to investigators a proposed informed consent form that complies with the ICH GCP guideline and regulatory requirements and is considered appropriate for this study. Any changes to the proposed consent form suggested by the investigator must be agreed to by Seqirus before submission to the IRB/EC and a copy of the approved version must be provided to the Seqirus monitor after IRB/EC approval.

### 13.3 Responsibilities of the Investigator and IRB/EC

The protocol and the proposed informed consent form must be reviewed and approved by a properly constituted IRB/EC before study start. Properly constituted IRB/EC is defined

in ICH Guideline for Good Clinical Practice E6 (R1), Section 3 ([ICH, 1997](#)), and Integrated Addendum to ICH E6(R2): Guideline for Good Clinical Practice ([ICH, 2016](#)). A signed and dated statement that the protocol and informed consent have been approved by the IRB/EC must be given to Seqirus before study initiation. Prior to study start and at any time the protocol is amended during study conduct, the Investigator is required to sign a protocol signature page confirming his/her agreement to conduct the study in accordance with these documents and all of the instructions and procedures found in this protocol and to give access to all relevant data and records to Seqirus monitors, auditors, Seqirus Clinical Quality Assurance representatives, designated agents of Seqirus, IRBs/ECs, and regulatory authorities as required. If an inspection of the clinical site is requested by a regulatory authority, the investigator must inform Seqirus immediately that this request has been made.

The Investigator also responsible for the following:

- Maintaining a list of appropriately qualified persons to whom the Investigator has delegated significant study-related duties
- Demonstrating the capability of recruiting the required number of suitable subjects within the recruitment period.
- Demonstrating sufficient time and staffing to properly conduct and complete the study within the agreed study period.
- Ensuring that all persons assisting with the study are adequately informed about the protocol, the investigational product(s), and their study-related duties and functions
- Ensuring that appropriately trained health care professionals are responsible for all study-related medical decisions and for ensuring appropriate medical care of subjects experiencing any adverse event related to the study
- If permission to do so is given by the subject (or legal representative), ensuring that the subject's primary healthcare provider is informed of the subject's participation in the study

The Investigator should not implement any deviation from, or changes of the protocol without agreement by the Sponsor and prior review and documented approval/favorable opinion from the IRB/IEC of an amendment, except where necessary to eliminate an immediate hazard(s) to study subjects, or when the change(s) involves only logistical or administrative aspects of the study (e.g. change in monitor(s), change of telephone number(s)). In addition, the Investigator, or person designated by the Investigator, should document and explain any deviation from the approved protocol.

The Investigator may implement a deviation from, or a change of, the protocol to eliminate an immediate hazard(s) to study subjects without prior IRB/IEC approval/favorable opinion. As soon as possible, the implemented deviation or change,

the reasons for it, and, if appropriate, the proposed protocol amendment(s) should be submitted:

- (a) to the IRB/IEC for review and approval/favorable opinion
- (b) to the Sponsor for agreement and, if required
- (c) to the regulatory authority(ies)

### **13.4 Protocol Amendments**

An amendment is a written description of change(s) to or formal clarification of a study protocol which may impact on the conduct of the clinical study, potential benefit of the clinical study, or may affect subject safety, including changes of study objectives, study design, subject population, sample sizes, study procedures, or significant administrative aspects. An administrative change of a study protocol is a minor correction or clarification that has no significant impact on the way the clinical study is to be conducted and no effect on subject safety (e.g. change of telephone number(s), logistical changes). Protocol amendments must be approved by Seqirus, health authorities where required, and the IRB/EC. In cases when the amendment is required in order to protect the subject safety, the amendment can be implemented prior to IRB/EC approval. Notwithstanding, the need for formal approval of a protocol amendment, the Investigator is expected to take any immediate action required for the safety of any subject included in this study, even if this action represents a deviation from the protocol. In such cases, Seqirus should be notified of this action, the IRB/EC at the study site, and, if required by local regulations, the relevant health authority) should be informed within 10 working days.

## **APPENDIX 1: EXAMPLES OF PRE-EXISTING MEDICAL CONDITIONS FOR CALCULATION OF RISK SCORE**

### **1. Pulmonary Disease**

- a. Asthma
- b. Chronic bronchitis
- c. Chronic obstructive lung disease or emphysema
- d. Pneumoconioses
- e. Pulmonary fibrosis
- f. Pulmonary tuberculosis and diseases due to other mycobacteria
- g. Sarcoidosis

### **2. Heart Disease**

- h. Coronary artery disease
- i. Valvular heart disease
- j. Congenital heart disease
- k. Hypertensive heart disease
- l. Ischemic heart disease
- m. Diseases of pulmonary circulation
- n. Myocarditis
- o. Arrhythmias, including atrial fibrillation
- p. Congestive heart failure

### **3. Renal Disease**

- q. Hypertensive renal disease
- r. Dialysis
- s. Renal transplantation
- t. Nephritis, nephrotic syndrome, nephrosis
- u. Chronic pyelonephritis
- v. Dialysis and transplant

### **4. Dementia or stroke**

- w. Neurologic and neurodevelopmental conditions [including disorders of the brain, spinal cord, peripheral nerve, and muscle such as cerebral palsy, epilepsy

(seizure disorders), stroke, intellectual disability (mental retardation), moderate to severe developmental delay, muscular dystrophy, or spinal cord injury].

- x. Cerebrovascular disease
- y. Dementia
- z. Hereditary and degenerative diseases of CNS

1. BACKGROUND AND RATIONALE

This document presents the statistical analysis plan (SAP) for Seqirus, Protocol No. V118_18: A Phase 3, Randomized, Double-Blind, Controlled, Multicenter, Clinical Study to Evaluate Safety and Immunogenicity of an MF59-Adjuvanted Quadrivalent Subunit Influenza Vaccine in Comparison with an MF59-Adjuvanted Trivalent Subunit Influenza Vaccine and an MF59-Adjuvanted Trivalent Subunit Influenza Vaccine Containing the Alternate B Strain, in Adults Aged 65 Years and Above.

The aim of this study is to demonstrate that inclusion of an additional B vaccine strain elicits an immune response to the second B virus and does not adversely impact the patient's immunogenicity response against strains previously included in trivalent formulations. Additionally, the aim is to demonstrate and confirm an acceptable safety and tolerability profile for the quadrivalent influenza vaccine formulation in the elderly population.

It describes the data and variables to be summarized and analyzed, including specifics of the statistical analyses to be performed. This analysis plan is based on the version 1.0 protocol dated 18 May 2017 and is compliant with ICH Harmonized Tripartite Guideline, 5 February, 1998, Statistical Principles for Clinical Trials, E9; World Health Organization, WHO Technical Report, Series No. 924. 2004, Annex 1: Guidelines on Clinical Evaluation of Vaccines: Regulatory Expectations; and FDA Center for Biologics Evaluation and Research (CBER) Guidance for Industry, May 2007, Clinical Data Needed to Support the Licensure of Seasonal Inactivated Influenza Vaccines.

The SAP provides the description of the analysis for the active study period and safety data through to the final evaluation (6 months following last study vaccination dose). Data from this study will be used to support the licensure of adjuvanted quadrivalent influenza vaccine (aQIV) for the prevention of seasonal influenza in adults ≥ 65 years of age.

2. STUDY OBJECTIVES AND ENDPOINTS

2.1 PRIMARY OBJECTIVES AND ENDPOINTS

2.1.1 PRIMARY OBJECTIVES

The co-primary immunogenicity objectives are:

1. To demonstrate that vaccination with aQIV elicits an immune response that is not inferior to that of an adjuvanted trivalent influenza vaccine (aTIV) containing the same virus strains as the US licensed adjuvanted influenza vaccine (Fluad, aTIV-1), and an aTIV containing the alternate B strain (aTIV-2) among adults ≥ 65 years of age.
2. To assess the immunogenicity of aQIV in adults ≥ 65 years of age, based on the CBER recommendations.

2.1.2 CO-PRIMARY ENDPOINTS

The immunogenicity of study vaccines will be assessed 21 days (i.e., on Day 22) after vaccine administration by measuring the hemagglutination inhibition (HI) antibody titers to the virus strains included in the vaccines.

The non-inferiority of aQIV compared to aTIV-1, and to aTIV-2 will be assessed for the eight co-primary endpoints of HI geometric mean titer (GMT) and seroconversion rate (SCR) for each virus strain included in the vaccines as follows:

- The GMT ratio* for the A/H1N1 strain;
- The GMT ratio for the A/H3N2 strain;
- The GMT ratio for the B strain (Yamagata lineage);
- The GMT ratio for the B strain (Victoria lineage);
- The difference between the SCR** for the A/H1N1 strain;
- The difference between the SCR for the A/H3N2 strain;
- The difference between the SCR for the B strain (Yamagata lineage);
- The difference between the SCR for the B strain (Victoria lineage).

Immunogenicity results obtained from aTIV-1 and aTIV-2 for both A/H1N1 and A/H3N2 strains will be pooled for comparison with aQIV.

*The GMT ratio is defined as the geometric mean of the post-vaccination (Day 22) HI titer for aTIV-1 (or aTIV-2) over the geometric mean of post-vaccination (Day 22) HI titer for aQIV.

**The SCR is defined as the percentage of subjects with either a pre-vaccination HI titer $< 1:10$ and a post-vaccination HI titer $\geq 1:40$ or a pre-vaccination HI titer $\geq 1:10$ and a ≥ 4 -fold increase in post-vaccination HI titer.

The second co-primary immunogenicity objective for aQIV will be assessed 21 days after vaccine administration by applying CBER criteria for the elderly population for each of the 4 strains included in aQIV. The second co-primary endpoints include:

- The percent of subjects achieving seroconversion (SC) for HI antibody
- The percent of subjects achieving an HI antibody titer $\geq 1:40$

The study is considered successful if all co-primary endpoints are achieved.

2.2 SECONDARY OBJECTIVES AND ENDPOINTS

2.2.1 SECONDARY IMMUNOGENICITY OBJECTIVES

The secondary objectives of the study are to assess the following, among adults aged ≥ 65 years:

1. To characterize the immunogenicity of aQIV, the aTIV-1 containing the same virus strains as the US licensed adjuvanted trivalent influenza vaccine, and the aTIV-2 containing the alternate B strain, by HI.
2. To demonstrate the immunological superiority of aQIV compared to aTIV-1 and aTIV-2 for the B strain that is not included in each TIV vaccine separately;

2.2.2 SECONDARY IMMUNOGENICITY ENDPOINTS

The secondary immunogenicity endpoints are:

- The measures of immunogenicity of aQIV, aTIV-1 and aTIV-2 used for Secondary objective 1 as determined by the HI assay against homologous strains at Day 1 and 22 (unless indicated otherwise), include the following:
 - GMT: Geometric mean of HI titers on Day 1(pre-vaccination) and Day 22 (post-vaccination);
 - Geometric mean ratio (GMR*): The geometric mean of the fold increase of post-vaccination HI titer over the pre-vaccination HI titer (Day 22/Day 1);
 - The percentage of subjects with a titer $\geq 1:40$ at Day 1 and Day 22;
 - SCR: the percentage of subjects with either a pre-vaccination HI titer $< 1:10$ and a post-vaccination HI titer $\geq 1:40$ or a pre-vaccination titer $\geq 1:10$ and a ≥ 4 -fold increase in post-vaccination titer.

* GMR is defined as the geometric mean of the fold increases of post-vaccination antibody titer over the pre-vaccination antibody titer.

- For Secondary objective 2, the immunologic superiority of the alternate B strain (e.g. the influenza B strain included in the aQIV but not in the aTIV formulation) in aQIV will be assessed for each aTIV separately, by using the co-primary endpoints of the ratio of HI GMT and the difference of SCR for each B virus strain 21 days after the last vaccination.

2.2.3 SECONDARY SAFETY OBJECTIVES

1. To assess safety and tolerability of aQIV, aTIV-1, and aTIV-2 among adults ≥ 65 years of age.

2.2.4 SECONDARY SAFETY ENDPOINTS

Safety and tolerability will be assessed by the frequency and severity of:

- Solicited local and systemic adverse events (AEs) for 7 days following vaccination (Day 1 through Day 7)
- All unsolicited AEs for 21 days following vaccination (Day 1 through Day 22) and medication associated with these events
- Serious AEs (SAEs), AEs leading to withdrawal from the study, new onset of chronic diseases (NOCDs), AEs of special interest (AESIs), and concomitant medications associated with these events as collected from Day 1 through Day 181.

2.3 EXPLORATORY OBJECTIVES

The exploratory immunogenicity objectives are:

1. To explore the association between HI immune response after administration of aQIV or the aTIV-1, containing the same virus strains as the US-licensed adjuvanted trivalent influenza vaccine, and the aTIV-2 containing the alternate B strain by baseline characteristics.
2. Additional optional objectives include characterization of the immunogenicity of aQIV using other immunological assays (e.g., virus neutralization [MN] or anti-neuraminidase antibody assays may be performed).

Both exploratory objectives may be performed using either homologous or heterologous strains, or both.

2.3.1 EXPLORATORY ENDPOINTS

The exploratory immunogenicity endpoints include:

- GMTs: Geometric mean HI titers (GMTs) at Day 1 and Day 22
- SCRs: Percentage of subjects with either a pre-vaccination HI titer $< 1:10$ and a post-vaccination HI titer $\geq 1:40$, or a pre-vaccination titer $\geq 1:10$ and a ≥ 4 -fold increase in post-vaccination titer at Day 22.
- In case of any additional optional immunogenicity analyses, such as MN, or assessments using heterologous influenza strains, the immune response will be characterized in a similar manner as described in the secondary immunogenicity endpoints section above.

2.4 SUCCESS CRITERIA

The study is considered successful if both co-primary objectives are achieved.

2.4.1 Success Criteria for Co-Primary Endpoints

2.4.1.1 To Demonstrate Non-Inferiority

In line with the FDA Guidance on seasonal inactivated influenza vaccines (Guidance for Industry Clinical Data Needed to Support Licensure of Seasonal Inactivated Influenza Vaccines 2007), aQIV will be considered to be non-inferior to aTIV-1, containing the same virus strains as the US licensed adjuvanted trivalent influenza vaccine, and aTIV-2, containing the alternate B strain if, for each of the four strains, the following statistical criteria are met:

- The upper bound of the two-sided 95% confidence interval (CI) for the ratio of the GMTs does not exceed 1.5. The GMT ratio will be calculated as $\text{GMT}_{\text{aTIV}}/\text{GMT}_{\text{aQIV}}$; and
- The upper bound of the two-sided 95% CI for the difference between the SCRs does not exceed 10%. The difference in SCRs will be calculated as $\text{SCR}_{\text{aTIV}} - \text{SCR}_{\text{aQIV}}$

2.4.1.2 CBER Criteria for Co-Primary Endpoints:

The endpoints for percent of subjects vaccinated with aQIV achieving SC and HI titer $\geq 1:40$ at Day 22 will be assessed against the criteria described in CBER Guidance Clinical Data Needed to Support the Licensure of Seasonal Inactivated Influenza Vaccines (FDA, 2007), namely

- The lower bound of the two-sided 95% confidence interval for the percentage of subjects achieving SC for HI antibody should meet or exceed 30%
- The lower bound of the two-sided 95% confidence interval for the percentage of subjects achieving a post-vaccination HI antibody titer $\geq 1:40$ should meet or exceed 60%

The statistical evaluation consists of the observed proportion together with the lower bound of the corresponding two-sided 95% CI per strain. No adjustment for type I error for multiplicity will be made.

2.4.2 Success Criteria for Secondary Objectives

2.4.2.1 Success Criteria for Secondary Immunogenicity Endpoints

There are no specific success criteria for the assessment of immunogenicity results (first secondary objective) as the characterization of the immunogenicity of the vaccines are descriptive in nature.

Superiority of aQIV versus aTIV-1 and aTIV-2 for the alternate B strain will be assessed using the GMT ratio ($\text{GMT}_{\text{aTIV}}/\text{GMT}_{\text{aQIV}}$) and difference in SCR ($\text{SCR}_{\text{aTIV}} - \text{SCR}_{\text{aQIV}}$) at Day 22. Point estimates and two-sided 95% CIs will be obtained as described for the primary endpoint. Superiority will be declared if the upper limit of the two-sided 95% CI for the difference in ($\text{SCR}_{\text{aTIV}} - \text{SCR}_{\text{aQIV}}$) is $< 0\%$, and the upper limit of the two-sided 95% CI for the GMT ratio ($\text{GMT}_{\text{aTIV}} / \text{GMT}_{\text{aQIV}}$) is < 1 for both B strains.

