#### 8.4.3.3.2 Analysis Sets

The secondary objective superiority testing will be performed using the Per Protocol Set (PPS).

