3. STUDY DESIGN

This phase 3 study is a randomized, double-blinded, comparator controlled, parallel-group, multicenter study of aQIV versus the US-licensed 2017-2018 adjuvanted trivalent influenza vaccine (aTIV-1, Fluad), and versus an adjuvanted trivalent influenza vaccine (aTIV-2), containing the alternate B strain. All study vaccine administration will be a single dose, and consistent with the current license for aTIV-1.

The study will be conducted in approximately 1778 male and female adults aged 65 years and older who are healthy or have co-morbidities which increase their risk of complications from influenza infection. Subjects will be randomized to one of the three treatment groups in a 2:1:1 ratio. An Interactive Response Technology (IRT) system will be used for subject randomization.

Subjects will provide serological specimens during the two mandatory clinic visits before and after vaccination on Day 1 and Day 22, respectively, for measurement of immune responses in routine influenza assays. Each subject will complete a Diary Card for solicited local and systemic AEs for 7 days after vaccination. Safety information will also be collected for all unsolicited AEs for 21 days following vaccination; and for the full duration of study participation for serious AEs (SAEs), AEs leading to withdrawal from the study NOCDs, AESIs, and concomitant medications associated with these events. Three scripted safety telephone calls will facilitate the collection of these safety data during the study period, and one reminder phone call will occur during the first few days after vaccination to remind the subject on the completion of the Diary Card.

An unscheduled study visit may be performed at any time during the study to further evaluate safety information described on the telephone.

Any subject who manifests signs of an influenza-like illness (ILI) during the treatment period (Days 1-22) will be evaluated by real time reverse transcription polymerase chain reaction (RT-PCR) testing of a nasopharyngeal (NP) specimen for influenza. Subjects with onset of ILI and RT-PCR-confirmed influenza during the treatment period (Days 1-22) will be removed from the Per Protocol Set (PPS) in the immunogenicity analyses. ILI will also be recorded as an AE.

For further details, please refer to section 3.0 of the protocol.

Table 3-1: Time and Events Table

Assessment	Clinic Visit 1	Reminder Phone Call	Safety Phone Call	Clinic Visit 2	Safety Phone Call	Safety Phone Call¹²

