7.3 Full Analysis Set (FAS) Immunogenicity

All subjects in the All Enrolled Set who are randomized, receive at least one study vaccination and provide immunogenicity data at Day 1 and Day 22.

The FAS will be used to produce summaries and listings of subject characteristics.

In case of vaccination error, subjects in the FAS Immunogenicity will be analyzed "as randomized" (i.e., according to the vaccine a subject was designated to receive, which may be different from the vaccine the subject actually received).

See section 4.1 for details on how to handle subjects randomized in the wrong stratum.

If a subject is unblinded during the study, he/she will be included in the FAS Immunogenicity.

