7.4 Per Protocol Set (PPS) Immunogenicity

The Per-Protocol Set (PPS) will comprise all subjects in the FAS Immunogenicity who do not have any PDs that are medically assessed as potentially impacting on immunogenicity results.

The PPS will be the primary set of interest for the primary/secondary immunogenicity analysis and a supporting analysis will be performed using the FAS Immunogenicity. Membership of the PPS will be determined prior to unblinding the study.

Duplicate tables of primary and secondary immunogenicity analyses may also be produced based on the FAS Immunogenicity if there is >1% difference in the total number of subjects between the PPS and the FAS Immunogenicity. The decision to produce tables based on the FAS Immunogenicity will be made by Seqirus after analysis sets are finalised and prior to unblinding.

Examples for subjects excluded due to other reasons than PDs are subjects who withdrew informed consent, and subjects with RT-PCR-confirmed ILI prior to Day 22, as documented by the central laboratory.

In case of misrandomization with regard to treatment arm, the subject is excluded from the PPS.

If a subject is unblinded during the study, except for SUSAR, he/she will be excluded from the PPS.

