11.2.3 Analysis Sets

The secondary objective superiority testing will be performed using the PPS.

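### Superiority for the alternate B strain is decided on the Per Protocol Set, whose exclusions tend to favour the claim; a cheap improvement is to decide it as randomized and settle how confirmed influenza is handled

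*SAP*

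**What the plan says.** The rule in SAP 2.4.2.1 begins "Superiority will be declared if the upper limit of the two-sided 95% CI for the difference in" SCR is below zero, and it names no analysis set. SAP 11.2.3 does: "The secondary objective superiority testing will be performed using the PPS". Protocol 8.4.3.3.2 says the same.

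Membership of the PPS depends on events after randomization:
- SAP 7.4 keeps subjects "who do not have any PDs that are medically assessed as potentially impacting on immunogenicity results". It also excludes subjects misrandomized with regard to treatment arm.
- SAP 6.1 lists receipt of the wrong treatment or an incorrect dose as a deviation category, and says that major deviations lead to exclusion from at least one analysis set.
- SAP section 3 says that subjects with RT-PCR-confirmed influenza in Days 1 to 22 "will be removed from the Per Protocol Set (PPS) in the immunogenicity analyses".

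SAP 7.3 defines the FAS Immunogenicity as subjects who are "randomized, receive at least one study vaccination and provide immunogenicity data at Day 1 and Day 22", analysed by assigned vaccine. SAP 7.4 and 8.2.2 give this set a supporting role. They add that duplicate tables may be produced if it differs from the PPS by more than 1% of subjects.

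The documents do not agree on confirmed influenza. SAP section 6 lists it among the criteria that exclude a subject from the FAS. SAP 7.3 does not mention it, and SAP 7.4 gives it as an example of an exclusion from the PPS. The protocol's Evaluable Set (Protocol 8.3.4), which also needs both samples, excludes it.

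**The concern.** In a non-inferiority test, leaving out deviators is the cautious choice, because they dilute the comparison towards no difference. In a superiority test the same exclusions remove dilution and so work in favour of the claim.

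Two kinds of exclusion act this way. Someone assigned aTIV who received a vaccine containing the missing B strain would raise the aTIV response if analysed as randomized. Someone assigned aQIV who received the aTIV without that strain would lower the aQIV response. Dropping either widens the gap. Likewise, an aTIV subject infected with the missing lineage may seroconvert to it, and dropping that subject lowers the aTIV result.

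At stake is a declared superiority claim that rests on a set shaped by post-randomization events, while the set closer to the randomized comparison does not decide it.

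**Working it through.** **Inputs from the documents** (SAP section 5 and Protocol 8.5): 800 aQIV v 400 aTIV for each B strain, SCR 40% for matched B strains, SD of log_e titer 1.2, one-sided alpha 0.025. Protocol section 1.1 puts type B at about 25% of positive specimens.

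**Assumptions** (the documents give no figure): aTIV SCR to the missing strain, share of subjects excluded, and titer rise on infection. Ranges are shown.

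**1. The plan's own figure.** For the B-strain SCR non-inferiority test, SE = sqrt(0.40 × 0.60/400 + 0.40 × 0.60/800) = 0.030. Power = Φ(0.10/0.030 − 1.96) = 91.5%, against 91.29% stated. No power is stated for superiority.

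**2. Shift in SCR.** If a fraction f of the aTIV arm consists of seroconverters who are removed, and the remaining subjects have SCR p, the SCR with them included is p(1 − f) + f. The shift is f(1 − p).
- f = 1%: 0.8 points at p = 20%, 0.7 at p = 30%.
- f = 4%: 3.2 and 2.8 points.

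**3. Does the verdict change?** Upper limit = (p − 0.40) + 1.96 × sqrt(p(1 − p)/400 + 0.24/800).
- With p = 30% and 16 of 400 infected seroconverters (4%) put back, aTIV is 32.8%, the difference −7.2, the half-width 5.7 and the upper limit about −1.5 points. Superiority is still declared.
- With p = 20% and the same 16 put back, the upper limit is about −11.5 points.
- The limit reaches zero at an aTIV SCR of about 34.2%. The number put back to get there is 400 × (0.342 − p)/(1 − p):

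| aTIV SCR without them | Number of 400 |
|---|---|
| 20% | about 71 |
| 30% | about 24 |
| 33% | 7 to 8 |

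**4. Error rate if there is no as-randomized difference (40% v 40%).** Remove a fraction f of aTIV, all seroconverters, and nobody from aQIV. The PPS aTIV SCR is (0.40 − f)/(1 − f), on 400(1 − f) subjects. For the GMT test, assume a 16-fold titer rise in those removed, with SE = 1.2 × sqrt(1/(400(1 − f)) + 1/800).

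| f | One SCR test | One GMT test |
|---|---|---|
| 0 | 0.025 | 0.025 |
| 1% | 0.039 | 0.057 |
| 2% | 0.060 | 0.113 |

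These are worst-case rates for a single test. The claim needs all four tests to pass.

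**5. Exclusions in both arms.** If 1% of each arm are infected seroconverters, with SCR 25% v 40%, the shifts are 0.75 and 0.60 points, a net of 0.15.

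**6. Is 4% realistic?** If type B makes up 25% of cases and every B case is the missing lineage, 4% of the arm with that lineage implies 4%/0.25 = 16% confirmed influenza in about three weeks.

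**The case against.** The strongest reply is that excluding infected subjects is partly a choice of question. The objective is the vaccine's response to the strain that each aTIV omits, and antibody from infection is not vaccine response. That stands for confirmed influenza, and it is why both versions should be reported. It does not cover wrong-vaccine or wrong-dose subjects, whose removal also takes out dilution.

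There are safeguards. "Membership of the PPS will be determined prior to unblinding the study", confirmed illness is documented by the central laboratory, exclusions go into a signed memo before unblinding, and a supporting FAS Immunogenicity analysis is planned. Blinding prevents selective exclusion. It does not stop exclusions from differing by arm, and the supporting analysis does not decide the claim. The FAS Immunogenicity also depends on having Day 22 data, so it is closer to the randomized comparison without being free of post-randomization selection.

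A reader might infer that SAP 7.3 already retains infected subjects, so that naming that set would be enough. The documents do not support this: SAP 7.3 is silent and SAP section 6 excludes them. A reader might also take a shift of up to 3.2 points against a half-width between 5 and 6 points as a threat to the claim. What counts is the distance of the upper limit from zero, and in step 3 the claim survives 4% from both 20% and 30%. Nor do the documents give any evidence that infection rates differ between arms by Day 22.

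**Conclusion.** The point holds as a minor one. The PPS decides superiority, its exclusions tend to favour that claim, and the as-randomized set is only supporting. The SAP also contradicts itself on whether confirmed influenza removes a subject from the FAS, so no superiority analysis is certain to keep those subjects.

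The effect is probably small: 0.7 to 0.8 SCR points per 1% of the aTIV arm removed, assuming that all those removed seroconverted, that none came from aQIV, and that the aTIV SCR is 20% to 30%. With aQIV at 40%, the SCR criterion fails only once the aTIV SCR reaches about 34%. The choice of set therefore matters only for a borderline result. Superiority is a secondary claim, and study success under SAP 2.4 does not depend on it.

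**What to change.** - In SAP 11.2.3 and Protocol 8.4.3.3.2, decide superiority on the FAS Immunogenicity analysed as randomized, with the PPS as supporting. State the set beside the rule in SAP 2.4.2.1.
- Leave the PPS as the deciding set for the co-primary non-inferiority tests.
- Reconcile SAP section 6 with SAP 7.3 and 7.4 on confirmed influenza, and align the protocol's Evaluable Set. SAP section 14 already says that the protocol will be updated to match the SAP's language.
- Report superiority both with and without confirmed-influenza cases, and say before unblinding which version decides.

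The cost is wording in both documents, a swap of two planned analyses and one further table. Sample size, data collection and conduct do not change. The downside is that the estimated aQIV advantage may be slightly smaller.
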